2.1.2 Secondary Objectives

- To measure gout flare frequency and health related quality of life.
- To assess treatment adherence measuring oxypurinol, the active metabolite of Allopurinol
- To evaluate the cost-effectiveness and safety of the approach by gathering data including hospital and GP visits and work absenteeism, and adverse events.
- Identification of uric acid load in faecal samples and correlation with gut microbiome characteristics.
- To assess feasibility of implementation, compliance and impact of dietary modification on serum urate levels.

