2.2 ENDPOINTS

2.2.1 Primary Endpoint

- Proportion of participants achieving urate level $\leq 0.30\text{mmol/L}$ at 24 weeks.

2.2.2 Secondary Endpoints (assessed at week 24 and 52, and for extension study also at week 104 and 156)

- Proportion of participants achieving urate level $\leq 0.3\text{mmol/l}$ and $\leq 0.36\text{mmol/l}$
- Prospectively gathered number of days of self-reported gout flare over course of study
- Size in mm of the largest tophus at baseline (index tophus)
- The number of clinically evident tophi
- Prospectively gathered self-reported quality of life during/following gout flare evaluated using the EQ-5D-5L questionnaire over course of study
- Prospectively gathered data on days lost at work due to gout flare over course of study
- Prospectively gathered number of scheduled and unscheduled medical appointments/ hospital admissions due to gout over course of study
- Self report of number of doses of medication omitted in preceding 2 weeks will be collected at all study visits
- Plasma oxypurinol levels will be measured at study visits where possible
- Proportion of patients achieving a dose reduction of urate lowering therapy in the extension phase whilst maintaining target urate levels.
- Proportion of patients achieving sustained dietary modifications with reduction of urate levels, and/or further reduction of urate lowering therapy dose in the extension phase.

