3 STUDY DESIGN

3.1 Original study

[figure not shown]
This is a feasibility study. A total of approximately 60 patients will be recruited from rheumatology clinics or rheumatology on-call services in NHS Lothian. Participants will be randomized to the intervention group in a 2:1 ratio. Based on baseline renal function and serum urate levels, and in line with local protocol, an individual treatment plan will be drawn up for all participants with the goal to achieve serum urate level of $\leq 0.30\text{mm/L}$. A sample from a 24 hour urine collection and paired serum creatinine and urate sample from each participant will be analysed for urate metabolites. The treatment plan will be communicated to the patient and their general physician.

All participants will have a smart phone application developed by IT specialists in the EPCC uploaded to their smart phones. Control participants will have a limited version of the GoutSMART application installed with background information about gout and providing a means for participants to enter details of gout flare frequency and quality of life through the trial. Subjects in the intervention group will be taught to self-test serum urate using a BeneCheck Plus hand held device and provided with test strips. A full version of the GoutSMART application will be installed with the features mentioned above but also incorporating advice on urate monitoring and medication titration. Participants will be prompted to check their serum urate on two separate days and enter the results into the GoutSMART application. The application will respond by a) a suggestion to increase urate lowering therapy or b) to stay on the current dose of allopurinol. If the patient needs to increase allopurinol there will be an automatic reminder two weeks after any increased dose of urate lowering therapy prompting the patients to test their own urate levels on two separate days and submit updated readings which will be handled in the same way as described above. Conversely for participants achieving target levels this will be acknowledged and a request to resubmit readings will be sent on a monthly basis until 3 consecutive target readings have been obtained. 6 months is given until review reflecting current practice.

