The main outcome will be urate levels at week 24, with a secondary outcome being urate levels at week 52. Where participants are able to attend hospital then both serum and capillary urate will be obtained and the serum urate will be used as the study outcome, however we anticipate that a capillary urate only will be obtained in participants required to self-isolate or maintain social distancing during the coronavirus pandemic and this will be used to determine the urate level at week 24 and 52 for affected participants. To assess treatment compliance drug metabolite levels will be tested from serum samples obtained at week 24 and 52 visits where possible, and by self report in all participants. All patients will be assessed for tophi at baseline by clinical exam, and again at week 24 and 52. This will be by examination if participants are able to attend hospital, or by review of submitted images where attendance at hospital is not appropriate due to coronavirus restrictions. All participants will be asked once per month to record flares, measurements of quality of life, number of hospital and GP visits as well as days off work via the application. The study is designed for a total (post-randomization) duration of 52 weeks. Subjects who withdraw or disengage before the 24 week visit will not be considered to have completed the study.

For the gut microbial aspect of this study, eligible participants will fill in an online semi-quantitative food frequency questionnaire (FFQ, Scottish Collaborative Group – see Zgaga et al, PLOSone 2012). Patients will also provide an early morning urine sample for urinary metabolomic analysis and a fresh faecal sample for subsequent faecal metabolomics and shotgun metagenomics. To provide suitable controls, patients will be asked whether they are happy that a family member be contacted to provide control samples for this analysis. In this case, first or secondary sex-matched controls without gout will be contacted by the study team for a once-off visit (Medical history, bloods – serum urate LFTs, renal function, FFQ and urine and stool samples). Patients can opt out of having a family member involved if they wish in which case local controls (age-similar and sex matched) will be recruited from the staff of the University of Edinburgh.

Figure 1: Study Design

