3.2 Extension phase

Urate-lowering therapy requires a long term commitment from the patient and health care provider. We know that levels of medication adherence in gout are unusually low (Dehlin M, 2017 and Briesacher BA, 2008). A recent randomised controlled trial comparing specially trained nurses leading care versus usual care in the UK, showed that with dedicated surveillance and monitoring, the use of urate lowering therapy is significantly higher at 1 and 2 years in the nurse-led compared to the usual care group (Doherty M, 2018). The GoutSMART approach may provide an alternative means for patients to monitor their disease and increase awareness of the role and importance of long-term urate lowering therapy for disease control thereby increasing adherence. At the 12 month study visit all participants will be invited to participate in a 2 year extension to the study which will evaluate long term compliance with medication along with clinical outcomes. Additional participants will be invited to take part in

this long term monitoring arm of the study and will be randomised 1:1 to active monitoring or routine care. All participants taking part in this extension study will have their medication optimised using the GoutSMART approach to ensure that their urate level is at target of 0.3mmol/l or less.

For participants in the active care arm of the study ongoing monitoring of self-reported urate will be performed until participants meet criteria for disease remission. For the purposes of this study we will define disease remission to have been achieved if all three of the following outcomes have been achieved:

[figure not shown]
- 1) Resolution of clinically evident tophi
- 2) Urate levels at or below 0.3mmol/l over preceding 12 months (with minimum of 3 separate readings obtained in different months).
- 3) Resolution of gout flares (self-reported) for 12 months

When remission has been achieved by these criteria then participants will be given the option to reduce their dose of allopurinol in line with current best practise guidelines which suggest that maintaining urate below 0.36 mmol/l is sufficient to maintain remission, and that long term urate levels should not be held below 0.18mmol/l.

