4.2 INCLUSION CRITERIA

Subjects must meet all of the following inclusion criteria to enter the study:

- Evidence of a personally signed and dated informed consent document indicating that the subject has been informed of all aspects of the study.
- Adult male or female aged ≥ 18 years.
- Confirmed clinical diagnosis of gout as per ACR/EULAR criteria (Neogi T, 2015).
- Physician recommendation that initiation or escalation of urate lowering therapy (Allopurinol or Febuxostat) is required guided by further monitoring of serum urate levels.
- No previous adverse reaction to Allopurinol or Febuxostat.
- Serum urate >0.36 mm/L.
- Patient has a smart phone and is able to use application.

For the gut microbiota part of this study control participants must be:

- Adult male or female aged ≥ 18 years.
- Evidence of a personally signed and dated informed consent document indicating that the subject (or a legally acceptable representative) has been informed of all aspects of the study.

For the extension study

- Patient has completed week 52 of original study
- Evidence of a personally signed and dated informed consent document indicating that the subject has been informed of all aspects of the extension study.

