6.1.2 Intervention procedures

Based on the baseline renal function and serum urate levels, and in line with local protocols, an individual treatment plan will be drawn up for all participants in both groups. This includes a management plan for a potential episode of gout-flare and offering of flare prophylaxis. The treatment plan will be sent to the general practitioner and the patient copied in. All participants will be examined at baseline and the number and size of tophi (if present) will be recorded.

All participants will have the GoutSMART application installed on their phones, and be taught how to use the application to allow direct communication between the research staff and the participant. All participants will be given access to online resources providing background information on the causes of gout, the likely progression of symptoms, strategies for dealing with acute attacks of gout and the importance of controlling serum urate levels. All participants will be prompted once per month to enter information about their disease severity including the number of days of flare per month, health related quality of life during and after flares, number of days lost at work and the number of health care appointments attended.

Participants in the intervention group will receive their treatment plan in the same fashion and will be provided with the BeneCheck hand-held device, taught to perform the serum urate finger prick self-test and shown how to enter this information into the application. Participants will be sent automatic reminders two weeks after any increased dose of urate lowering therapy (including that of the plan set during baseline clinic consultation) to test their own urate levels and submit updated readings. If urate levels remain above target, written advice to increase the dose of urate lowering will be sent to the patient and supervising physician advising up-titration of therapy, with this confirmed also by text message. If up-titration is recommended, a reminder to test again will be sent after a further two weeks. Conversely, for participants achieving target levels, acknowledgement will be sent and a request to resubmit readings will be sent on a monthly basis until three consecutive target readings have been obtained. Six months are allowed to ensure that all participants have the opportunity to escalate to maximum therapy and potentially switch to alternative urate lowering therapy if required.

6.1.3 End-of study visit week 24

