8.2 PROPOSED ANALYSES

The primary outcomes of the study will be the proportion of participants achieving urate level $\leq 0.3\text{mmol/l}$ at 24 weeks in participants receiving supported self-management compared to those receiving usual care. Comparison of proportions will be performed using the Chi-square test of independence, or Fishers Exact test for where expected values in any cell of the contingency table are less than 5, with results displayed as frequency (percentages). The proportion of participants achieving serum urate level $\leq 0.3\text{mmol/l}$ at all subsequent assessments will be analysed in the same fashion. Patients with undetectable levels of oxypurinol will be deemed to be non-compliant and a similar analysis will compare the proportion of participants in each treatment allocation that are non-compliant. For these analyses an intention to treat analysis will be performed with participants that have dropped out of the study being included as failing to reach target, or non-compliant with medication respectively.

Continuous outcome measures include the size in mm of the largest tophus at baseline (index tophus) measured at 52 weeks, and the number of clinically evident tophi evaluated at 52 weeks. Further continuous outcomes include the number of days lost at work due to gout flare, number of scheduled and unscheduled medical appointments/ hospital admissions, self report of number of doses of medication omitted in 2 weeks prior to study visits at week 24 and 52. Two-tailed independent student t-tests will be applied for between group comparisons of normally distributed data. Results will be displayed as mean \pm standard deviation (SD). A Mann Whitney U test (MWU) will be applied when the variables are not normally distributed, with results given as median (interquartile range IQR). Although a nominal value of significance of $p<0.05$ for these exploratory measures will be adopted, given the number of secondary outcomes listed a Bonferroni correction will be applied and reported alongside each result.

Although health reported quality of life data will be gathered this is exploratory data that will not be analysed directly but be used to inform the design of a larger health economic study.

Statistical analysis will be performed using Minitab version 16 (Minitab Inc., Pennsylvania, US) or the Statistical Package for Social Services version 19 (SPSS IBM Corp, NY State, US).

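### The undetectable-oxypurinol rule in Section 8.2 is not limited to allopurinol users, so adherent febuxostat users with a result are counted as non-compliant

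*Combined protocol and SAP*

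**What the plan says.** Section 8.2 gives one binary definition of non-compliance: "Patients with undetectable levels of oxypurinol will be deemed to be non-compliant". The proportion is compared between arms by chi-square or Fisher's exact test, by intention to treat, with dropouts counted as non-compliant.

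Section 2.1.2 gives the purpose of the assay: "To assess treatment adherence measuring oxypurinol, the active metabolite of Allopurinol". Section 3.1 says that "drug metabolite levels will be tested from serum samples obtained at week 24 and 52 visits where possible".

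Febuxostat is within the study. Section 4.2 requires a physician's recommendation that "initiation or escalation of urate lowering therapy (Allopurinol or Febuxostat) is required". Section 6.1.2 allows six months so that participants can "escalate to maximum therapy and potentially switch to alternative urate lowering therapy if required".

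A second adherence measure does not depend on the drug. Section 2.2.2 states: "Self report of number of doses of medication omitted in preceding 2 weeks will be collected at all study visits". Section 8.2 analyses it separately, as a continuous outcome at weeks 24 and 52.

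**The concern.** An assay for the metabolite of one drug is used to judge adherence in everyone, including participants who may be prescribed another drug. If an adherent participant takes febuxostat, the expected oxypurinol result is undetectable, and Section 8.2 then records non-compliance. Nothing in the documents exempts febuxostat users or gives them another compliance class.

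Adherence is a named secondary objective, and long-term compliance is a stated purpose of the extension. The oxypurinol rule is the only adherence proportion that Section 8.2 compares between arms. The study is also meant to inform the design of a larger one. An artefact of drug choice could therefore be read as an effect, or a lack of effect, of supported self-management on adherence.

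**Working it through.** **Step 1: does the rule misclassify?** Four kinds of participant with an oxypurinol result, under the rule as written:

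| Drug | Truly adherent? | Oxypurinol expected | Scored as | Correct? |
|---|---|---|---|---|
| Allopurinol | yes | detectable | compliant | yes |
| Allopurinol | no | undetectable | non-compliant | yes |
| Febuxostat | yes | undetectable | non-compliant | **no** |
| Febuxostat | no | undetectable | non-compliant | yes |

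The febuxostat rows rest on the description of oxypurinol in Section 2.1.2; the documents do not say outright that febuxostat yields none. The table treats the assay as perfect for allopurinol.

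**Step 2: effect of one misclassified participant.** With all n participants of an arm in the denominator, the shift is 100/n percentage points. Group sizes are from Section 8.1.

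- Extension: 100/20 = 5.0 and 100/30 = 3.3.
- Original study: 100/34 = 2.9 (intervention) and 100/17 = 5.9 (control).

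This step needs no assumed febuxostat share.

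**Step 3: direction of the distortion.** Let f be an arm's febuxostat share, and assume that adherence does not depend on the drug. Then observed adherence = true adherence × (1 − f). With the 90% and 50% of Section 8.1 and an assumed f of 10%:

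- Both arms: 0.90 × 0.90 = 81% vs 0.50 × 0.90 = 45%. The difference falls from 40 to 36 points.
- Smart-care arm only: 81% vs 50%. The difference falls to 31 points.
- Usual-care arm only: 90% vs 45%. The difference rises to 45 points.
- No true difference (90% in both), febuxostat in one arm only: 81% vs 90%. A difference of 9 points is created.

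**Step 4: one illustration of power.** First, the plan's own figures. Section 8.1 states 81% power at 20 per arm and 94% at 30 for 90% vs 50%. The normal approximation with pooled variance gives 0.813 and 0.943 (two-sided 5%, a level that Section 8.1 states for the primary outcome and that is assumed here for the extension). The stated figures are therefore correct from their inputs.

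Next, exact enumeration of the test in Section 8.2 (Pearson chi-square, or Fisher if any expected count is below 5), with everyone sampled and no dropout:

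| Febuxostat share, both arms (assumed) | Observed adherence | Power, 20 per arm | Power, 30 per arm |
|---|---|---|---|
| 0% | 90% vs 50% | 83% | 95% |
| 10% | 81% vs 45% | 68% | 84% |

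The table applies only if the 90% and 50% are measured by the oxypurinol rule, which Section 8.1 does not say.

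**The case against.** The strongest reply is that this is in practice an allopurinol study. The application's maintenance advice is "to stay on the current dose of allopurinol", and in remission "participants will be given the option to reduce their dose of allopurinol". Section 2.1.2 itself ties the assay to allopurinol, so a sensible analyst might not apply the rule to febuxostat users. This stands as a reason why the effect may be small or nil. It does not cure the text: Sections 4.2 and 6.1.2 keep febuxostat in the study, and Section 8.2 has no restriction. A choice made once drug use by arm is known would also leave open whether such participants are excluded or reclassified. Because the drug can change after randomisation, excluding them would break the intention-to-treat comparison.

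A second reply is that self-reported omitted doses are collected from everyone and compared between arms. That also stands: oxypurinol is not the only adherence comparison. But the self-report does not override the binary rule, and Section 8.2 names its analysis only at weeks 24 and 52.

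A reader might infer more than the documents support:

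- **That every febuxostat user makes adherence look worse.** Only an adherent one does.
- **That the extension is underpowered because of this rule.** Section 8.1 does not say how its adherence is measured. One of its two benchmarks is a medicine possession ratio, which is not a metabolite assay.
- **That the bias has a known direction.** More switching in the actively titrated arm is plausible, but no drug share by arm is given.
- **That lower powers obtained by adding dropout or missing samples belong to this point.** Those losses have other causes.

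**Conclusion.** The rule in Section 8.2 is wrong as written and should be corrected: it scores adherent febuxostat users with a result as non-compliant. Confidence in that is high, since it follows from Sections 2.1.2, 4.2, 6.1.2 and 8.2 read together.

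The size that can be stated without an assumed febuxostat share is the shift per participant in Step 2, between 2.9 and 5.9 points depending on the group. The total effect is unknown. The fall in power in Step 4 is an illustration that rests on an assumed 10% share in both arms and on an unconfirmed link to the extension's sample size; it is not a forecast.

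The consequence is limited to a secondary outcome in a feasibility study. The primary urate endpoint does not use the rule.

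**What to change.** In Section 8.2:

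1. Apply the undetectable-oxypurinol rule only to participants prescribed allopurinol at that visit.
2. Classify febuxostat users by a cut-off on self-reported omitted doses, fixed before the data are analysed.
3. Keep all randomised participants in the comparison, and keep the existing dropout rule.
4. Report the drug split by arm at each assessment.

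A sensitivity analysis that applies the self-report criterion to everyone is optional.

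**Cost.** The self-report is already collected at every visit. The current drug must be taken from the electronic patient record, which Section 7.1 lists as a source, or recorded at each visit; the documents do not say that it is recorded each time. The change needs a cut-off to be chosen and an amendment through the approvals in Section 12.1. The main downside is that the endpoint would mix a biochemical and a self-report criterion, so some misclassification could return if drug shares differ by arm. The optional sensitivity analysis would examine that.

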4 STUDY POPULATION

4.1 NUMBER OF PARTICIPANTS

We aim to recruit approximately 60 participants. Recruitment will remain open until sufficient numbers of recruited participants has been reached. Additional participants satisfying the same inclusion and exclusion criteria (but without any urate threshold requirement) will be recruited into the extension study to ensure sufficient power is maintained). An equal number of control participants will be recruited for the purposes of the gut microbiota analysis.

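### Week-52 index tophus size and tophus count are compared without adjusting for the recorded baseline values, which gives up precision and lets chance baseline imbalance into the estimate

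*Combined protocol and SAP*

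**What the plan says.** Section 8.2 states the two tophus outcomes as week-52 values. For size it names "the size in mm of the largest tophus at baseline (index tophus) measured at 52 weeks". For tophus burden, the outcome given is "the number of clinically evident tophi evaluated at 52 weeks". The tests are the same as for the other continuous outcomes: "Two-tailed independent student t-tests will be applied for between group comparisons of normally distributed data". Otherwise the rank test is used: "A Mann Whitney U test (MWU) will be applied when the variables are not normally distributed".

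Section 2.2.2 likewise lists the size of the index tophus and the number of tophi, with no change from baseline.

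The baseline values will exist. Section 6.1.2 says: "All participants will be examined at baseline and the number and size of tophi (if present) will be recorded". Section 3.1 has tophi assessed again at weeks 24 and 52. No section uses the baseline values as a covariate, in a change score, or as a stratification factor at randomisation. Nor does 8.2 say which participants form the analysis set for either outcome.

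**The concern.** The index tophus is chosen and measured at baseline, so its later size can be expected to depend to some degree on its starting size. Comparing raw week-52 sizes leaves that variation in the error term. In a small group, any difference in starting size that arises by chance then appears, in part, as if it were a difference between arms.

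The count has a related weakness. Participants with no tophi at entry can enter as zeros, and most would probably be zero again at week 52. The raw comparison would then partly reflect how many participants in each arm had tophi at the start.

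Sections 8.1 and 13.2 say that the study is meant to inform a larger trial. What is at stake is the quality of the tophus estimate and its confidence interval as inputs to that trial.

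**Working it through.** **The plan's own figure.** The documents give no power or precision figure for the tophus outcomes. The 82% in section 8.1 concerns the primary endpoint. It reproduces with the continuity-corrected formula (82.0% at 14 v 28, after 15% drop-out from 17 v 34) but says nothing about tophi.

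**Inputs from the documents.** Recruitment target: "We aim to recruit approximately 60 participants" (section 4.1). Allocation 2:1 to the intervention (sections 3.1 and 8.1).

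**Assumptions not in the documents.**
- Share with a baseline tophus: 20%, 30% or 40% of 60, i.e. 12, 18 or 24 participants, split 8 v 4, 12 v 6 or 16 v 8. No drop-out is applied.
- Correlation r between baseline and week-52 size within arm: 0.3, 0.5 or 0.7.
- True effect: 0.8 SD. Two-sided 5% test.

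**Step 1: chance baseline difference.** Its standard error, in baseline SDs, is √(1/n₁ + 1/n₀).

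| Split | Standard error | Chance that it exceeds 0.5 SD |
|---|---|---|
| 8 v 4 | √(1/8 + 1/4) = 0.61 | 41% |
| 12 v 6 | √(1/12 + 1/6) = 0.50 | 32% |
| 16 v 8 | √(1/16 + 1/8) = 0.43 | 25% |

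**Step 2: how much of it reaches the raw estimate.** With equal SDs at the two visits, a baseline difference of b SD shifts the expected raw week-52 difference by r × b. For b = 0.5 this is 0.15 SD at r = 0.3, 0.25 SD at r = 0.5 and 0.35 SD at r = 0.7. With no treatment effect, baseline imbalance accounts for r² of the variance of the raw difference: 9%, 25% and 49%.

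**Step 3: precision.** Relative to raw week-52 values, the variance under ANCOVA is 1 − r² and under a change score 2(1 − r).

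| r | ANCOVA | Change score | Sample-size equivalent of ANCOVA, 1/(1 − r²) |
|---|---|---|---|
| 0.3 | 0.91 | 1.40 | 1.10 |
| 0.5 | 0.75 | 1.00 | 1.33 |
| 0.7 | 0.51 | 0.60 | 1.96 |

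A change score would be worse than the raw comparison at r = 0.3 and no better at r = 0.5, so ANCOVA is the form to use.

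**Step 4: power at these sample sizes.** These figures come from simulation with normal data and include the degree of freedom spent on the covariate. Ranges reflect separate runs.

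| Split | Raw t-test | ANCOVA, r = 0.3 | r = 0.5 | r = 0.7 |
|---|---|---|---|---|
| 12 v 6 | about 32% | about 33% | 38-39% | 52-54% |
| 8 v 4 | about 22% | 21-22% | 25-26% | 34-35% |

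If r is zero, ANCOVA loses one to two percentage points.

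**Step 5: false positives.** In 20,000 simulated null trials per setting (5 v 10 and 9 v 17; r = 0.5, 0.7, 0.9), the raw t-test rejected in 4.7-5.3% overall. In the 5 v 10 trials where the baseline difference exceeded 0.5 SD, it rejected in 8%, 11% and 14% at r = 0.5, 0.7 and 0.9. ANCOVA stayed at about 5-6% in the same trials.

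**The case against.** The strongest reply is that r may be low here. Section 1.1 says that tophi resolve when urate is held low, so some treated index tophi may reach 0 mm whatever their starting size. Section 3.1 allows later assessment from submitted images instead of examination, which adds measurement error. One simulation with resolution built in (assumed 50% v 15%, 12 v 6) gave a within-intervention correlation of about 0.32 and power of 36% for the t-test, 34% for Mann-Whitney and 41% for ANCOVA. At 8 v 4 the figures were 27%, 23% and 29%. This stands: the gain may be small, and zeros make a purely parametric ANCOVA questionable for size.

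It is also true that adjustment does not make the outcome well powered. Section 8.2 reports a Bonferroni correction beside each result. If eight outcomes are assumed, power at 12 v 6 is 10% raw, 13% at r = 0.5 and 21% at r = 0.7. Section 8.2 calls these measures exploratory, and neither the sample size nor the primary endpoint depends on them.

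A reader might go further and infer that baseline imbalance drives the result, or that the planned test is biased. The documents do not support that. Arms are randomised and the overall type I error is about 5%. Imbalance accounts for about half or more of the null variation only if r is about 0.7 or higher, and the documents give no r.

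A reader might also infer that participants without a tophus will enter the size analysis as zeros. Nothing in the plan proposes this, and such a participant has no index tophus to measure. The analysis set for size is merely unstated.

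**Conclusion.** The point holds as a matter of efficiency and of bias conditional on the imbalance that happens to occur, not as a flaw in the validity of the comparison. The plan collects the baseline values that would sharpen both tophus comparisons and does not use them.

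The benefit runs from none at r = 0.3 to about 20 percentage points of power at r = 0.7 with 12 v 6 (32% to 52-54%), or about 12 points with 8 v 4 (22% to 34-35%). That range rests on assumed values for the share with tophi, the correlation and the effect size. That the group with tophi is small is itself an inference from the target of about 60 and from size being recorded only where a tophus is present. What does not depend on these assumptions is that 8.2 uses no baseline value and names no analysis set. The primary conclusion is unaffected.

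**What to change.** In section 8.2:

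- **Index tophus size.** Analyse participants with a baseline tophus, scoring a resolved tophus as 0 mm, by ANCOVA with baseline size as covariate. Use a rank-based ANCOVA if the data are skewed or contain many zeros.
- **Tophus count.** Include baseline count as a covariate, in a rank-based analysis or a count model, and state who is included.
- **Reporting.** Show baseline size and count by arm and give the adjusted difference with its 95% confidence interval. Keep the t-test or Mann-Whitney test as a check.

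The cost is wording and a little more analysis work, with no new data or visits. Statistically it costs one degree of freedom and, if the correlation is near zero, the one to two points of power noted above.
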